5.3. PURPOSE OF THE DEVICE

The “In-Clinic LVAT” test was designed to automatically determine the pacing threshold of a preselected set of LV pacing vectors in subjects implanted with a Platinum SonR CRT defibrillator. This feature is available only when the ICD (Platinum SonR CRT-D) is interrogated by a programmer (Orchestra Plus) equipped with a 2.54 C1 SmartView clinical version (or upgraded version). This function has no effect on the standard use of the CE-marked commercialized implant Platinum SonR CRT-D device.

[figure not shown]
5.4. FEATURE USE

The “In-Clinic LVAT” function is capable to measure automatically the pacing threshold values of all LV pacing vectors selected by the physician, instead of a one by one manual test (as performed in routine practice). It is composed of several consecutive individual tests called LV Vector Tests.

Before launching this function, the physician needs to program a temporary configuration comprising of a pacing configuration, starting pacing amplitude, and pacing width.

Thereafter, all LV Vectors Tests are performed sequentially. More precisely, the LV Vector Test 1 starts by launching the function and decrementing automatically the LV pacing amplitude, in order to determine the threshold value. In turn, the following LV Vector Test is automatically launched by modifying automatically the LV pacing vector programming, and so on until the last LV Vector Test. All these steps are performed automatically, and results are displayed on the programmer screen to be exploited by the physician.

Flowchart of test functioning:

“In-Clinic LVAT” tests are detailed in the Investigator Brochure (Appendix A).

6. STUDY PROCEDURES

Prior to investigational site activation or involvement in study activities, all personnel participating in the study must be trained on the investigational feature, the CIP and the study-specific electronic data capture (EDC) system. It may also include GCP training, if necessary, and can only be provided by dedicated and experienced staff (sponsor or sponsor delegated staff). All study-specific trainings will be documented and filed at both site and sponsor level.

The study feature should be used in accordance with the corresponding Instructions For Use (IFU) (MISC3606).

Detailed guidelines on data to be recorded for the study, and how to fill in the eCRFs in the EDC system will be provided to the Investigators.

6.1. TREATMENT AND EVALUATION

6.1.1. *Inclusion follow-up*

Subjects must be informed about the investigation and the potential benefits and risks of the study prior to enrollment. Only those subjects who voluntarily provide written consent to participate will be eligible for enrollment.

The following procedures must be conducted before inclusion of the subject in the study:

- Evaluate subject eligibility based on the inclusion and exclusion criteria
- Obtain written informed consent
- Source data that demonstrate conformance with inclusion criteria should be retained at the investigational site

The following procedures must be conducted in order to include the subject in the study:

- Report implant information
- Report subject's medical history
- Report subject's clinical examination including current vital signs and NYHA classification
- Report subject's current concomitant medications (based on the EDC questions)

6.1.2. *M0 follow-up*

- Perform a complete interrogation of the device with the appropriate clinical programmer
- Print report file
- Measure P-R, A-R and V-V inter ventricular conduction durations on the EGM
- Launch manual LV threshold tests on:
 - 5 common LV vectors to IS1 and IS4 for all subjects,
 - 4 dedicated IS4 LV vectors for subject implanted with IS4 LV lead (LV2-LV4, LV3-LV4, LV3-LV2, LVtip1-LV4).

Manual tests should be performed prior to automatic test to limit bias.

Optional manual threshold tests on additional LV pacing vectors could be performed under physician discretion.

- ECG record:
 - Spontaneous rhythm,
 - Paced rhythm during “In-Clinic LVAT” test in DDD A-test for 30 seconds recording corresponding to 10 seconds before launching test and 20 seconds during the test.
- Launch “In-Clinic LVAT” test on all LV pacing vectors in following pacing configuration:
 - DDD A-test
 - DDD P-test
 - VVI
- Perform right ventricular pacing recordings data collection using RF telemetry to allow collection of multiple EGM:
 - RV A-test

- RV P-test
- Retrieve subject technical data analysis files
- Report Adverse Events and Serious Adverse Events occurred during the testing procedure if any
- Report Device Deficiencies if any

6.1.3. M1 follow-up

- Perform a complete interrogation of the device with the appropriate clinical programmer
- Print report file
- Measure P-R, A-R and V-V inter ventricular conduction durations on the EGM
- Launch manual LV threshold tests on:
 - 5 common LV vectors to IS1 and IS4 for all subjects,
 - 4 dedicated IS4 LV pacing vectors for subject implanted with IS4 LV lead (LV3-can, LV3-RVring, LV3-RVcoil, LV4-RVcoil).

Manual tests should be performed prior to automatic test to limit bias.

Optional manual threshold tests on additional LV pacing vectors could be performed under physician discretion.

- ECG record:
 - Spontaneous rhythm,
 - Paced rhythm during “In-Clinic LVAT” in DDD A-test for 30 seconds recording corresponding to 10 seconds before launching test and 20 seconds during the test.
- Launch “In-Clinic LVAT” test on all LV pacing vectors in following pacing configuration:
 - DDD A-test
 - DDD P-test
 - VVI
- Perform right ventricular pacing recordings data collection using RF telemetry to allow collection of multiple EGM:
 - RV A-test
 - RV P-test
- Retrieve subject technical data analysis files
- Report Adverse Events and Serious Adverse Events occurred during the testing procedure if any
- Report Device Deficiencies if any
- Report Serious Cardiovascular Adverse Event occurred since last follow-up if any

6.1.4. *Unscheduled follow-ups*

If the subject comes in due to a serious cardiovascular adverse event, re-intervention, or if the subject’s device is interrogated for any reason outside of regular follow-up, the routine follow-up procedure should be performed when possible.

6.2. STUDY CONCLUSION

All study and printout reports should be on document and retrieved on the subject's medical file.

Next subject follow-up will be scheduled by the physician according to his/her standard clinical practice.

Study completion for a subject will occur after he/she has completed M1 follow-up.

6.3. PREMATURE SUBJECT WITHDRAWAL OR DISCONTINUATION

For subjects lost to follow-up, the Principal Investigator must ensure all reasonable efforts have been made to contact the subject to return for a CIP-required follow-up. These efforts shall be documented. It is expected that the Principal Investigator and site personnel will act in an ethical manner to encourage each subject to complete the study.

For subjects discontinued by the Principal Investigator for safety reason, the Principal Investigator shall document the reasons for his/her decision.

6.4. SUBJECT STUDY TERMINATION RECORD

A study termination record must be completed and signed by the Principal Investigator for each subject enrolled in the study. The study termination record will capture the reason for study termination (e.g. early termination, lost to follow-up, study completion).

7. RISK ANALYSIS

7.1. POTENTIAL & RESIDUAL RISKS

The risk analysis and the risk mitigation of the investigational feature are detailed in the Investigator Brochure (Appendix A). The main risks include the following:

- Anodic stimulation or fusion leading to under-estimation of the pacing threshold
- Inappropriate or absence of back up pacing leading to long ventricular cycle
- Slow VT detection temporarily turned off during the test leading to inability to detect Slow VT during the test

These risks are all mitigated by design and are considered acceptable.

The Global Product Analysis of the device supporting the feature under investigation (Ref. AR00523 and AR 00503) did not identify any significant additional risk related to device use.

The procedures required by the CIP do not differ from routine follow-up practice, except for the launch of the "In-Clinic LVAT" tests which is not expected to lead to other risks than the ones associated to standard threshold pacing tests.

7.2. POTENTIAL BENEFITS

Platinum SonR CRT-D implant offers the same potential clinical benefits for subject as any commercial CRT implantable defibrillator.

However, subjects who are participating to the study will not have direct benefits from the clinical evaluation, although they will have a comprehensive assessment of electrical performances of their left ventricular lead. Nevertheless, once marketed, this automatic tool will allow physician to identify and program the optimal configuration of subject device in a timely manner.

7.3. MITIGATION

To protect the welfare of subjects, ethics committee and/or competent authority approval of the investigation will be obtained for each site prior to the first implant at that site.

Investigators selected to participate in this study will have experience in the follow-ups of CRT-D systems. Trained and experienced LivaNova representatives will be made available to support follow-ups and in case of troubleshooting.

Training will be provided to the investigators and their staff to ensure that the CIP and study procedures and instructions to be performed are understood and will be applied.

Each investigator will sign an Investigator Agreement stating his/her responsibility to conduct this study according to this investigational plan, to adhere to the records and reporting requirements, and to supervise use of the investigational device.

Through careful design and testing, LivaNova has attempted to minimize the risk to subjects. Testing included bench testing or device performance and software validation testing.

Risks can be minimized through compliance with the CIP, using the devices in accordance with their applicable Instructions for Use, performing the procedures following recommended standard practices/guidelines, performing procedures in the appropriate hospital environment, adherence to subject selection criteria, close monitoring of the subject's status and by promptly supplying the Sponsor with all pertinent information required by this CIP.

7.4. RISK-TO-BENEFIT ANALYSIS

The Sponsor believes that the value of the knowledge to be gained by conducting this clinical study to evaluate LEVEA outweighs the potential risks posed to the participating subjects. There is no anticipated increased risk related to the participation in the study.

8. STATISTICAL CONSIDERATIONS

The statistical analysis will be performed as mentioned in this CIP and detailed in the Statistical Analysis Plan (SAP). Endpoints and time points are described in the other CIP sections.

Any relevant major change to the statistical analysis requested after CIP approval must be defined and approved through a CIP amendment or must be clearly mentioned in the statistical plan of the study in a section 'Changes in the conduct of analyses from CIP', including the rationale of changes.

8.1. SAMPLE SIZE CALCULATION

The study primary objective will be met in case the null hypothesis that the success rate of the "In-Clinic LVAT" is at least than 90% is be rejected.

The statistical analysis of primary endpoint will be performed on the ITT population (see section 8.2).

A sample size of at least 231 evaluable LV pacing vectors (configuration) will provide 80% power to reject the trial null hypothesis by using a one-sided alpha 2.5% and assuming an expected success rate of 95% – configuration based. As each subject can provide data on 5 different pacing vectors, 47 (~231/5) subjects are needed for the statistical analysis. Accounting for a global attrition rate of 20%, 59 subjects shall be enrolled.

8.2. ANALYSIS POPULATION

The analysis populations will be reviewed and determined during the Data Review meeting based on all included subjects. The included population will consist of all subjects who have completed "Inclusion Form".

The main analysis populations are:

- The Intention To Treat (ITT) population will consist of all included subjects with at least 1 eligible complete LV Vector Tests at M0 follow-up (if unavailable, M1 follow-up will be considered). This population will be used for the assessment of the primary endpoint (see section 4.1.2).
- The M0-Intention To Treat (M0-ITT) population will consist of all included subjects with at least 1 eligible complete LV Vector Tests at M0 follow-up. This population will be used for the assessment of the secondary endpoints concerning the LV test done at M0 follow-up (see section 4.1.3).
- The M1-Intention To Treat (M1-ITT) population will consist of all included subjects with at least 1 eligible complete LV Vector Tests at M1 follow-up. This population will be used for the assessment of the secondary endpoints concerning the LV test done at M1 follow-up (see section 4.1.3).
- The included population will be used for the assessment of the secondary endpoint “Applicability of the algorithm” (see section 4.1.3).
- The safety population will consist of all subjects included and implanted with Platinium SonR CRT-D 1811, 1841 or 1844. The number of subjects in each population will be mentioned in the disposition of subjects.
- Ancillary population will consist of all included subjects with at least one right ventricular pacing electrogram collected during RV A-test or RV P-test at M0 or/and M1 follow-up (see section 4.1.4).

8.3. GENERAL STATISTICAL CONSIDERATIONS

According to the type of parameters, the summary results will be presented at least as follows:

- Continuous parameters: number and percentage of subjects with available and missing data, mean, standard deviation (SD), median, quartiles (Q1, Q3), and the extreme values (Minimum; Maximum).
- Categorical and ordinal data: number and percentage of subjects. For some specific categorical data as adverse events, number of events and the number of subjects having at least one event (morbidity or mortality) will be presented. In case of ordinal parameter, descriptive statistics will be performed as a quantitative parameter if relevant.

8.4. DEMOGRAPHICS AND SUBJECT CHARACTERISTICS

Description of subjects, including subjects' characteristics and medical history will be summarized to describe the study population.

8.5. ANALYSIS OF PRIMARY, SECONDARY AND ANCILLARY ENDPOINTS

8.5.1. Primary endpoint

The trial null hypothesis is that the success rate of the “In-Clinic LVAT” feature is lower than 90%. The alternative hypothesis is that the success rate of the “In-Clinic LVAT” feature is at greater than or equal to 90%.

The Primary endpoint is discussed in details in Section 4.1.2.

A one-sided exact binomial test for proportion at 2.5% level of significance (alpha) will be performed to test the null hypothesis for the primary endpoint. The null hypothesis will be rejected if the p-value is less than 0.025.

Handling of Missing values/censoring/Discontinuations

The primary endpoint will primarily be based on the completed LV Vector Tests provided by the algorithm and collected at M0. If data at M0 is unavailable, then corresponding data collected at M1 will be considered. If data at both M0 and M1 is missing, no imputation will be done.

Supportive Analysis of the Primary Endpoint

- i. The estimate of the success rate will be presented along with exact 95% confidence interval (CI) (Clopper & Pearson, 1934). [2]
- ii. Bayesian analysis will be performed to calculate the probability that the success rate is greater than or equal to 90%. A non-informative prior for the success rate ($\sim \text{Beta}(1, 1)$) will be assumed. Thus, if x successes out of n completed LV vector tests is observed, then success rate will have a posterior distribution $\text{Beta}(x+1, n-x+1)$. A 95% credible interval will also be calculated for the success rate.

8.5.2. Secondary and ancillary endpoints

Secondary and ancillary endpoints will be assessed at all follow-ups using descriptive statistics. Point estimates and 95% CI will be presented wherever possible.

8.6. SAFETY ANALYSIS

The secondary objective of assessing safety and device deficiencies of the compound will be answered by summarizing the relevant endpoints by means of descriptive statistics on the Safety population.

9. DATA MANAGEMENT

9.1. CASE REPORT FORMS (CRFs), DATA REVIEW, DATABASE CLEANING, ISSUING AND RESOLVING QUERIES

The Principal Investigator and authorized site personnel must enter the information required by the CIP on the eCRF. Data are to be entered into a clinical database as specified in the Data Management Plan (DMP). Quality control and data validation procedures are applied to ensure the validity and accuracy of the clinical database.

The Principal Investigator is responsible for maintaining adequate and accurate medical records from which accurate information is recorded onto electronic CRFs (eCRFs) from an Electronic Data Capture (EDC) system developed by the EDC vendor. All CIP-required data, unless otherwise specified, will be recorded on eCRFs or, if requested, provided in an electronic format (e.g., device settings data). All eCRFs and electronic data must be handled in accordance with instructions from the Sponsor and submitted to the Sponsor in a timely fashion. At the end of the study, the Principal Investigator may request a copy of the eCRFs. All data will have separate source documentation; no data will be recorded solely onto the eCRF.

All CRF data sent to the Sponsor must be endorsed by the Principal Investigator.

Data will be reviewed according to the Data Management Plan (DMP) in order to perform the database cleaning. Data are to be reviewed and checked for omissions, errors, and values requiring further clarification using computerized and manual procedures. In case of inconsistencies, inaccurate data or other discrepancies, data queries will be generated for those data points requiring clarification from the site.

After resolution of all inconsistencies and discrepancies, a global data review will be performed in order to prepare the final study database. The final locked database will be provided for the statistical analysis.

9.2. VERIFICATION, VALIDATION AND SECURING OF ELECTRONIC CLINICAL DATA SYSTEM

Study data will be entered into a Clinical Data Management System (CDMS) as specified in the Data Management Plan (DMP). The software used for data management should be reliable, and documentation of appropriate software testing procedures should be available. Quality control and data validation procedures are applied to ensure the validity and accuracy of the clinical database. Access to the study data will only be given to authorized and trained users, and all corrections are documented in an auditable manner.

10. SAFETY REPORTING

The Sponsor is responsible for the ongoing safety evaluation of the investigational device, review of reported adverse events (AE), investigation of Unanticipated Serious Adverse Device Effects (USADE), and notification of regulatory authorities per applicable requirements. The Sponsor is also responsible for training the investigational staff prior to start the study on any study-related procedures, including reporting of Serious Adverse Events (SAE).

The Sponsor, through the Clinical Safety Office, will provide oversight of general AE handling procedures for the clinical study and can assist the investigators and various committees in conducting a medical review of reported serious adverse events.

The Principal Investigator is responsible for ensuring the safety and well-being of the subjects enrolled in their clinical sites and should report events to the Sponsor, Ethics Committees, and regulatory bodies as described in this section.

10.1. DEFINITIONS

Adverse events definitions are derived from ISO 14155:2011 - Clinical investigation of medical devices for human subjects. The definitions of the following terms can be found in the glossary (section 14):

- Adverse Event – AE
- Adverse Device Effect – ADE
- Device deficiencies
- Serious Adverse Event – SAE
- Serious Adverse Device Effect - SADE
- Unanticipated Serious Adverse Device Effect –USADE

10.2. PRINCIPAL INVESTIGATOR'S RESPONSIBILITIES IN ADVERSE EVENT REPORTING

The responsibilities of the principal investigator include the following:

- The Principal Investigator is required to report the following adverse events to the Sponsor:
- Unanticipated Serious Adverse Device Effects should be reported to the Sponsor within 24 hours of awareness of the event by notifying the Sponsor Clinical Project Manager and by entering the information in the EDC. These events require urgent investigation by the Sponsor and reporting to regulatory authorities, as applicable.
- All adverse events (serious and non-serious) during the testing procedure should be reported. However, conditions that occur due to direct physiologic effects of testing (e.g. PNS, palpitations, and discomfort) are not considered adverse events.
- Serious cardiovascular and access site adverse events from inclusion (signing date of informed consent) to termination should be reported as soon as possible but no later than 3 calendar days upon awareness. The Principal Investigator should enter all available information in the “AE section” of the EDC system. Cardiovascular events refer to those that are classified under cardiac disorders, bleeding disorders, cerebrovascular, and peripheral vascular as defined in the trial-specific AE classifications (Appendix B).
- Device deficiencies should be reported within 5 calendar days of awareness. Deficiencies of the Sponsor study device should be reported in the Device Deficiencies section in EDC. The Principal Investigator must return the device, if possible, to the Sponsor. Deficiencies of the non-Sponsor study device should be reported following the commercial reporting procedure for that device.

Timelines and Communication Methods for Reporting Adverse Events

Study Period	Event Classification	Communication Method	Communication Timeline
During initial testing procedure	All adverse events e.g. procedural complications (serious and non-serious), excluding direct physiologic effects of testing	Complete AE eCRF page with all available information.	Within 3 calendar days of first becoming aware of the event
Throughout study duration	All Serious cardiovascular and access site Adverse Events	Complete AE eCRF page with all available information.	Within 3 calendar days of first becoming aware of the event
Throughout study duration	All deaths	Complete AE eCRF page with all available information. Provide all relevant source documentation (unidentified) for reported event	Within 1 business day of first becoming aware of the event.
Throughout study duration	Unanticipated (Serious) Adverse Device Effect	Complete AE eCRF page with all available information. Provide all relevant source documentation (unidentified) for reported event	Within 1 business day of first becoming aware of the event. Reporting of any updated information required through the end of the study
Throughout study duration	Device Deficiencies (including but not limited to failures, malfunctions, and product nonconformities) with or without associated adverse events	Complete Device Deficiency eCRF with all available new and updated information	Within 5 days first becoming aware of the event and as per local/regional regulations Reporting required through the end of the study

- The Principal Investigator should perform the following assessments for each reported serious adverse event:
 - Identify the clinical event (Diagnosis or symptoms),
 - Seriousness of the event,
 - Relationship of the event to the device and/or procedure.
- The Principal Investigator should provide all the information needed to complete the AE electronic CRF.

- The Principal Investigator is responsible for informing the Ethics Committee, and regulatory authorities of serious adverse events as required by local/regional regulations.
- The Principal Investigator is expected to assist in clinical review and supply the Sponsor with relevant source documents and results of ancillary procedures required in the CIP.

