- Serious adverse device events and device deficiencies will be collected during each subject follow-up. Confirmation of absence of USADE during “In-Clinic LVAT” tests will be evaluated by analyzing all SAEs and device deficiencies collected at each follow-up.
- The focus of the “In-clinic LVAT” deficiencies will include:
 - o Assessment of pacing threshold underestimation: comparison to manual LV threshold value will be performed by comparing manual and automatic LV threshold values at each follow-up. An underestimated LV threshold value of “In-Clinic LVAT” feature is defined as a value result more than 2 steps below the LV threshold measured manually. For all the eligible complete LV Vector Tests collected, only manual LV threshold test performed in the same conditions and reported in the electronic Case Report Form (eCRF) will be retained. Only one LV Vector Test per LV pacing vector per subject will be analyzed. In case several LV Vector Tests are eligible with the same LV pacing vector, for the same subject, on the same follow-up, only the last one will be considered.
 - o Confirmation of absence of unexpected function operations by analyzing EGM and ECG performed during “In-Clinic LVAT” test at each follow-up. Any unexpected function operation will be reported.

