14.1. GENERAL RULES FOR AE REPORTING

Adverse events that occurred after the inclusion visit and prior to study termination or Lost-to follow-up will be presented for all subjects in the Safety Population.

If there are less than 10 Adverse events reported in the study, the Adverse Events will be reported only by listing.

The following Safety Events will be reported in the study based on their time of occurrence:

During initial testing procedure

- All adverse events e.g. procedural complications (serious and non-serious), excluding direct and clinically expected physiologic effects of testing

Throughout the study

- All Serious cardiovascular and access site Adverse Events
- All deaths

LEVEA – Statistical Analysis Plan

- Unanticipated (Serious) Adverse Device Effect
- Device Deficiencies (including but not limited to failures, malfunctions, and product nonconformities) with or without associated adverse events

The classification of AEs for statistical analysis will be based on site-reported events for the final diagnosis in the Safety populations.

A positive relationship (YES) will include those assessed as related or unknown if related to the device/procedure. A negative relationship (NO) will be limited to those assessed as not being related to the device/procedure.

The adverse events (AEs) in the Safety population will be assessed using descriptive statistics by

- Diagnosis (AE Category, AE Term, AE clarifiers)
- Relationship – (Yes/No)
- Device Interrogation (Yes/No)
- Treatment and Medication
- Outcome (Resolved/Death/Pending)
- Relationship: to procedure, to device
- Expectedness for ADE (Yes/No)

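### Protocol 10.2 keeps direct physiologic effects of testing out of the adverse event definition with no limit on seriousness, contrary to the protocol's own glossary and more broadly than the SAP

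*Protocol*

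**What the plan says.** - **Protocol 10.2, text.** "All adverse events (serious and non-serious) during the testing procedure should be reported". The next sentence narrows this: "conditions that occur due to direct physiologic effects of testing (e.g. PNS, palpitations, and discomfort) are not considered adverse events".
- **Protocol 10.2, reporting table.** The row for the initial testing procedure repeats the exclusion: "All adverse events e.g. procedural complications (serious and non-serious), excluding direct physiologic effects of testing".
- **Protocol 10.2, other rows of the table.** These apply throughout the study and state no exclusion: "All Serious cardiovascular and access site Adverse Events"; deaths; unanticipated serious device effects; and "Device Deficiencies (including but not limited to failures, malfunctions, and product nonconformities) with or without associated adverse events".
- **Protocol 10.1 and 14.** Section 10.1 sends the reader to the glossary for the definitions. There an AE is any unwanted medical event, whether or not it is related to the device, and a note adds events related to the procedures. An ADE is defined as a kind of AE, a SADE as a kind of ADE, and a USADE as a SADE not foreseen in the risk analysis report.
- **Protocol 4.1.3(e).** Absence of USADE during the automatic tests "will be evaluated by analyzing all SAEs and device deficiencies collected at each follow-up". SAP 11.1(A) repeats this.
- **SAP 14.1.** For the initial testing procedure all AEs are reported, "excluding direct and clinically expected physiologic effects of testing". SAP 3.1, on changes from the protocol, reads as not applicable.

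**The concern.** The sentence in Protocol 10.2 does more than spare sites the paperwork for trivial sensations. It says that a class of conditions are not AEs at all, and the class is defined by mechanism. The three examples are mild, but they are introduced as examples, and nothing confines the rule to mild, non-serious or expected effects. In the table the exclusion directly follows a phrase covering serious and non-serious events, so on its face it applies to both.

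The harm most directly caused by the test is therefore the harm that the clause most clearly removes. The safety endpoint has two inputs, SAEs and device deficiencies, and the first could be incomplete because of the definition. A statement that no USADE occurred would be weaker than it looks.

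**Working it through.** No arithmetic applies, because the point depends on no rate, power or sample size. The check sets the passages side by side.

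| Place | Effects of testing excluded from AEs | Limited by seriousness? | Limited to expected effects? |
|---|---|---|---|
| Protocol 14 (glossary) | None; procedure-related events are included | – | – |
| Protocol 10.2, text | All direct physiologic effects | No | No |
| Protocol 10.2, table, initial testing row | All direct physiologic effects | No | No |
| SAP 14.1 | Effects both direct and clinically expected | No | Yes |

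1. **Within the protocol.** Section 10.1 adopts the glossary definition and section 10.2 departs from it. Both cannot govern the same event.
2. **Protocol against SAP.** An effect that is direct but not clinically expected is excluded under Protocol 10.2 and reportable under SAP 14.1. SAP 3.1 does not record the difference.
3. **Which wording decides the data.** SAP 14.1 bases AE classification on what sites report, and sites work from the protocol. The narrower SAP wording cannot restore an event that was never entered.
4. **How the exclusion carries through.** An event that is not an AE cannot be an SAE or an ADE. One that is not an ADE cannot be a SADE, and one that is not a SADE cannot be a USADE. The main loss is in the AE, SAE and SADE counts. USADE is affected only where the event goes beyond the risk analysis in kind, frequency, severity or result, since an event already foreseen there is not a USADE anyway.
5. **Other reporting routes.**
   - The rows for serious cardiovascular events and for unanticipated device effects carry no exclusion, but an event must first be called an AE to enter either.
   - Deaths have their own row, which does not depend on AE status.
   - Device deficiencies are reported with or without an AE, so a device fault is captured. A physiologic reaction to a test that ran as designed need not be a deficiency. In SAP 14.2 the link from a deficiency to harm is whether it led to an adverse event, which again depends on AE status.
   - The EGM and ECG review for unexpected operations (Protocol 4.1.3(e), SAP 11.1(C)) records how the function behaved. It does not record what happened to the subject.
   - The independent reviewer in Protocol section 11 looks at threshold data. No independent adjudication of events is described.

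The gap that remains is a serious, non-fatal event during a test with no device fault, which a site attributes directly to the test.

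**The case against.** Read in context, the clause is probably meant for the ordinary sensations of threshold testing. Its examples are phrenic nerve stimulation, palpitations and discomfort, and the sentence before it asks for serious as well as non-serious events. An experienced investigator might well report a serious event regardless. This is fair as to intent, but the wording does not secure it, and the sponsor's own SAP adds a qualifier that the protocol lacks.

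A reader might go further and infer that harm from the risks listed in Protocol 7.1 can never be counted. The documents do not support that.

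- Section 7.1 does not describe any of its risks as a direct physiologic effect of testing.
- Under-estimation of the threshold is a measurement error with its own endpoint in Protocol 4.1.3(e).
- Slow VT that is missed while detection is off is not plainly an effect of pacing.
- The risk worded "Inappropriate or absence of back up pacing leading to long ventricular cycle" may be a malfunction, and is then reportable as a device deficiency. That symptoms from such a pause would fall under the exclusion is an inference; the documents name no such symptoms.
- Risks already in the risk analysis are largely anticipated, so harm from them is mostly outside USADE with or without the clause.

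It can also be said that a change now would come late. SAP version 1.0 is dated 19 February 2018, and SAP 17.8 names an M0/M1 extract whose file name carries the date 20180112. This suggests that much of the testing was done. It affects which remedy is useful, but the inconsistency remains.

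**Conclusion.** The point holds as an inconsistency with a practical consequence. Protocol 10.2 excludes direct physiologic effects of testing from AEs without regard to seriousness or expectedness, contradicts the protocol's glossary, and is broader than SAP 14.1. A site that applies it literally could leave a serious test-induced event out of the AE, SAE and SADE counts, and so out of one of the two inputs to the safety endpoint. Such an event may go uncounted; it is not certain to.

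The size cannot be given as a number. The documents hold no rate of serious events during testing and no basis for guessing how sites read the clause. Counts of tests per subject, or an upper bound from zero events among the 59 planned subjects, would describe exposure or precision and not the number of events lost.

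The conclusion assumes that neither the AE classification (Protocol Appendix B) nor the Investigator's Brochure limits the exclusion. Neither is reproduced in the documents.

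**What to change.** - Reconcile Protocol 10.2 (text and table), the glossary AE definition in section 14, and SAP 14.1. The exclusion should cover only non-serious, clinically expected effects, and no event that meets the SAE definition should be excluded.
- Record the wording difference between protocol and SAP in SAP 3.1.
- If visits are already complete, query sites for serious events left unreported under this clause, and state the limitation beside any claim that no USADE occurred.

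The cost is a protocol amendment or clarification with ethics committee handling; Protocol 12.6 requires committee approval before an amendment is implemented. Beyond that there would be matching SAP text, possibly a few more AE pages, and one round of site queries if the change comes after the visits.
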